### **Ethical Statement**

The study will adhere to the Ethical Principles of Psychologists and Code of Conduct set by the BACP and BPS. Ethical approval will be granted by the South Yorkshire Research Ethics Committee (24/YH/0055) and the UK Health Research Authority. The study will be registered on ClinicalTrials.gov (NCT06451965).

### **Analysis**

Both single-case visual and statistical techniques will be used following best practices (Harrington & Velicer, 2015; Manolov & Moeyaert, 2017). Visual analysis will assess phase variability using a  $\pm 25\%$  stability envelope (Lane & Gast, 2014). Higher percentages will indicate greater stability, and lower percentages will reflect greater variability.

To assess whether VAS ratings during the intervention phase are higher than baseline, Tau-U (Parker et al., 2011) will be implemented. It will account for baseline trends, effect sizes, and phase non-overlap. Resistant to autocorrelation, Tau-U provides strong statistical power in small datasets (Parker et al., 2014). Interpretations will follow Vannest and Ninci's (2015) guidelines, with baseline corrections applied as needed to prevent inflated effect sizes.

Piecewise regression (Center et al., 1985) will complement Tau-U findings by quantifying change over time within each phase. Level and slope changes will be examined, estimating the breakpoint for outcome improvements. This approach will model level shifts and gradual trends while considering data variability and abrupt changes (Tate & Perdices, 2018).

To address autocorrelation, lag-1 autocorrelation will be assessed, and if detected, Generalised Least Squares (GLS) regression with an AR(1) structure will be applied (Somer et al., 2022).

Reliable change in PHQ-9 will be measured via the Reliable Change Index (RCI; Jacobson & Truax, 1991), with Cronbach's  $\alpha = 0.79$  (De Man-Van Ginkel et al., 2012) and a stroke sample SD of 5.1 (Strong et al., 2021). Clinically Significant Change (CSC) will not be determined due to limited non-clinical-normative data for stroke populations. Given concerns about the comparability of PHQ-9 scores between stroke and non-stroke populations (Blake et al., 2025), data from other populations will not be considered. Instead, a cut-off of 10 will be applied to approximate clinically meaningful change, based on validated studies (De Man-Van Ginkel et al., 2012; Negeri et al., 2021; Williams et al., 2005).

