## **Evaluation of the Wisdom Enhancement Timeline Approach for Post-Stroke Depression Using a Single-Case Experimental Design**

[name]1a, [name], [name]

**Date:** 26/03/2024

This study will aim to answer the question: *Does enhancing wisdom through the timeline technique improve mood in post-stroke depressed individuals?* Additionally, it will examine whether enhancing wisdom restores identity continuity and improves self-esteem.

It is hypothesised that wisdom will improve first, followed by gains in identity clarity or self-esteem, as structured self-reflection fosters agency and self-worth. Finally, mood regulation is expected to improve last, aligning with findings that emotional stabilisation follows meaning-making and self-affirmation rather than occurring simultaneously (Beaumont, 2009).

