#### **Participants**

Three participants will be recruited, meeting SCED standards (Epstein et al., 2021; Kratochwill et al., 2013) through local stroke services. Inclusion criteria will require adults with post-stroke depression (PSD) who can provide informed consent and engage in therapy. Exclusion criteria will include severe cognitive or mental health impairments, medical instability, substance dependency, concurrent psychological treatment, participation in clinical trials, or newly prescribed psychotropic medication that has not yet stabilised. Participants who start psychotropic medication during the trial will remain eligible, as SCED analysis can account for medication-related changes.

NHS clinical teams will identify eligible participants, seeking permission for the researcher to contact them, while the author will conduct eligibility assessments and deliver the intervention. After the baseline phase, participants will attend six weekly sessions, either in person at a hospital or online via video conference.

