#### **Idiographic Visual Analogue Scale**

The primary outcome will be assessed using a Visual Analogue Scale (VAS), a widely used measure

for tracking subjective experiences in clinical research (McCormack et al., 1988). Participants will rate their agreement with four daily statements on vertically presented 10 cm scales, with higher scores indicating stronger agreement. VAS items will be aligned with the research questions and reviewed for relevance by individuals with lived stroke experience via the university's Personal and Public Involvement (PPI) database.

The four VAS items will be:

1. Today, my mood is good (VAS\_mood)
2. Today, I feel able to accept the person I am/Today, I feel like I am adapting to life after my stroke (identity; VAS\_ID)
3. Today, I feel good about myself (self-esteem; VAS\_SE)
4. Today, I feel that I can use the wisdom of my life to help me deal with my current problems (VAS\_wisdom)

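### The visual-analysis rule reads every low percentage inside the ±25% envelope as variability, without naming the envelope's centre line; around a flat phase level, a large improvement within the phase would be read as scatter.

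*Combined protocol and SAP*

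**What the plan says.** The Analysis section opens with the visual analysis: "Visual analysis will assess phase variability using a" ±25% stability envelope. The next sentence gives the only rule for reading the result: "Higher percentages will indicate greater stability, and lower percentages will reflect greater variability". The section names no centre line for the band and no percentage above which a phase counts as stable. It lists no separate measure of stability around a trend.

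Three other statements bear on the point.
- The opening hypotheses set an order of change: "wisdom will improve first, followed by gains in identity clarity or self-esteem", and "mood regulation is expected to improve last".
- The Analysis section says of the piecewise regression: "This approach will model level shifts and gradual trends". It describes that regression as "quantifying change over time within each phase".
- The data are "four daily statements on vertically presented 10 cm scales" (Idiographic Visual Analogue Scale section), and after baseline "participants will attend six weekly sessions" (Participants section).

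**The concern.** A percentage taken around a flat level mixes two things: scatter from day to day, and movement of the level during the phase. The reading sentence assigns all of it to scatter. The plan allows for movement within the intervention phase. It expects outcomes to improve in sequence with mood last, it estimates a breakpoint for improvement, and Table 1 places reflection on timeline events at session 3, after two sessions of information gathering and psychoeducation.

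The stability percentage is the only visual-analysis measure the plan names, and there are three participants, so each one's visual description will be prominent. A participant with a large, smooth gain could be described as variable beside a regression showing a clear slope, and the plan has no rule for reconciling the two. Because the centre line is unstated, two analysts could also report very different percentages from the same ratings.

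**Working it through.** The plan states no stability percentage, so there is no figure to reproduce. The check asks what the rule returns under each possible centre line.

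**Inputs from the plan.** Band of ±25%; daily ratings on a 10 cm scale; six weekly sessions.

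**Assumptions.** 6 × 7 = 42 ratings in the intervention phase, none missing; the start and end scores shown; independent normal noise with SD 0, 0.5 or 1.0 cm.

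**1. Flat centre, straight rise from a to b, no noise.** The median is (a + b)/2, so the band is 2 × 0.25 × (a + b)/2 = 0.25(a + b) wide. The scores span b − a. Hence

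share inside = min{1, 0.25(a + b)/(b − a)}.

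The share is 100% while 0.25(a + b) ≥ b − a, that is, while b/a ≤ 1.25/0.75 = 1.67.

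| Rise (cm) | Ratio b/a | Formula | 42 daily points |
|---|---|---|---|
| 4 to 6 | 1.50 | 100% | 100% |
| 3 to 5 | 1.67 | 100% | 100% |
| 3 to 6 | 2.00 | 0.25 × 9/3 = 75% | 30/42 = 71% |
| 3 to 7 | 2.33 | 0.25 × 10/4 = 62.5% | 26/42 = 62% |
| 2 to 6 | 3.00 | 0.25 × 8/4 = 50% | 20/42 = 48% |

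A phase flat at 2 cm for 14 days and then rising to 6 cm has 10/42 = 24% inside. Centring on the mean instead of the median gives 62%, 48% and 26% for the 3-to-7, 2-to-6 and delayed 2-to-6 cases.

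**2. Trend-line centre, same band width.** Every straight rise in the table has 100% inside.

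**3. With noise** (simulated, 2,000 series per row, band width ±25% of the phase median, split-middle trend line).

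| Noise SD | Phase (cm) | Around median | Around trend line |
|---|---|---|---|
| 0.5 | flat at 5 | 98.7% | 98.6% |
| 0.5 | flat at 3 | 86.7% | 86.6% |
| 0.5 | 4 to 6 | 89.4% | 98.6% |
| 0.5 | 3 to 7 | 60.3% | 98.5% |
| 1.0 | flat at 3 | 55.6% | 56.3% |
| 1.0 | 4 to 6 | 71.6% | 79.3% |
| 1.0 | 3 to 7 | 55.4% | 79.2% |

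At SD 1.0 the level-based figure cannot separate a phase flat at 3 cm from a rise of 3 to 7 cm: both are near 55%. The trend-based figure does separate them (56% against 79%).

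**4. Abrupt change, no noise.** A step exactly at the phase boundary leaves 100% inside in each phase. A step inside the phase does not. For 2 to 6 cm on day 29, 28 of the 42 ratings equal the median, so 28/42 = 67% lie inside the median band. Around a least-squares line the figure is 26% to 43%, depending on how the band width is defined.

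**The case against.** The strongest objection is that the premise is not in the plan. The Analysis section never says that the band surrounds a flat level, and around a trend line the steady-rise problem disappears. That stands, and it is why the conclusion is conditional. The silence does not settle the matter, though, because the reading sentence is unconditional whichever line is used.

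A reader might go further and infer that a participant who improves steadily, as the plan expects, will be reported as unstable. The documents do not support that reading.
- No cut-off or stable/unstable class is given. The participant would receive a lower percentage, read as more variability, and no label.
- The hypotheses predict an order of change, not a steady rise, and the regression also provides for level shifts.
- Moderate steady rises, such as 3 to 5 or 4 to 6 cm, stay wholly inside without noise.

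Nor can one infer that a responder will look more variable than a non-responder with the same noise. A 3-to-7 cm rise scores 60% at SD 0.5, against 99% for a phase flat at 5 cm but 87% for one flat at 3 cm. At SD 1.0 the gap to flat at 3 cm vanishes. It even reverses for a rise of 4 to 6 cm (72%) against flat at 4 cm: there the band is ±0.25 × 4 = ±1 cm, or ±1 SD, which holds about 68%.

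Two further objections stand in part. The percentage drives no phase change or effect test, and within-phase slope is modelled separately, so the harm is limited. Moving every band to a trend line would also have costs: a drifting baseline would score as fully stable around its own trend, and a large abrupt step would score worse than it does around the median.

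**Conclusion.** The point holds as a conditional, descriptive weakness. The plan reads any low percentage as variability while leaving the centre line unstated. With a flat centre (median or mean), a within-phase improvement of roughly twofold or more lowers the percentage without any noise: to 71% for 3 to 6 cm, 62% for 3 to 7 cm and 48% for 2 to 6 cm. At SD 0.5 the choice of centre alone moves the 3-to-7 cm result from 60% to 98.5%. Without noise, rises up to a ratio of about 1.67 are unaffected.

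These figures rest on 42 complete ratings and on assumed scores and noise SDs; the plan gives no VAS level or SD. Tau-U and the piecewise regression do not use the percentage, so the estimates of effect are untouched. Only the visual-analysis description is at risk. This is a minor point, worth correcting because it takes so little.

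**What to change.** In the Analysis section:
1. State the centre line of the ±25% envelope and how its width is computed.
2. For each phase, report the percentage around the phase level and the percentage around that phase's fitted trend line, with the direction of the trend.
3. Reword the reading sentence so that a low level-based percentage is called variability only when the trend-based percentage is also low and the plot shows no abrupt shift within the phase. If phases are to be labelled stable or variable, fix the percentage that separates them in advance.

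The cost is a few sentences of wording and one more descriptive figure per phase, from the same ratings and plots. A straight trend line fits a large abrupt step poorly, which is why the level-based figure should be kept beside it and not replaced.

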### **Methods**

#### **Design**

A single-case experimental multiple-baseline design (MBD) will be adopted. Following Christ's (2007) recommendations, the study will pre-specify hypotheses, predetermine baseline durations, and randomise allocation via Random.org. Participants will be assigned to baseline durations of 2, 3, or 4 weeks, with non-concurrent intervention introduction to enhance flexibility. The independent variable will be the intervention, and the dependent variables will be mood, wisdom, identity, and self-esteem, measured repeatedly. Blinding will not be implemented due to feasibility constraints.

Although stability is generally recommended before intervention, Krasny-Pacini and Evans (2018) suggest that five baseline data points are sufficient to distinguish natural fluctuations from intervention effects. Replication will be built into the multiple-baseline design, with each participant serving as an independent test of the intervention's effects. Initially, a one-month follow-up review will be planned; however, this may be omitted if time does not permit.

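### Tau-U is called resistant to autocorrelation, but its standard variance assumes independent ratings, and the plan corrects only the regression, and only when autocorrelation is detected

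*Combined protocol and SAP*

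**What the plan says.** The Idiographic Visual Analogue Scale section makes the VAS the primary outcome and has it completed every day: "Participants will rate their agreement with four daily statements". Under Design, "Participants will be assigned to baseline durations of 2, 3, or 4 weeks". Under Participants, after baseline "participants will attend six weekly sessions".

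The Analysis section gives the between-phase comparison to Tau-U, with the stated purpose "To assess whether VAS ratings during the intervention phase are higher than baseline". Its justification is "Resistant to autocorrelation, Tau-U provides strong statistical power in small datasets". The only adjustment planned for Tau-U is for trend: "baseline corrections applied as needed to prevent inflated effect sizes". Piecewise regression is described as complementing Tau-U. A separate paragraph deals with serial dependence: "lag-1 autocorrelation will be assessed, and if detected, Generalised Least Squares (GLS) regression with an AR(1) structure will be applied".

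The plan gives no test or threshold for that check. It also gives no Tau-U variance formula, alpha or sidedness, no expected autocorrelation, and no statement on whether Tau-U p-values or intervals will be reported.

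**The concern.** Daily ratings from one person are likely candidates for positive serial correlation, and the plan itself provides for it in the regression. The same series feed Tau-U, which is exempted by assertion.

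The assertion mixes two properties. Autocorrelation does not shift the expected value of Tau-U when there is no effect, so the point estimate stays centred at zero. It does make the estimate more variable than the independence formula says, so p-values are too small and intervals too narrow. Removing a baseline trend does not remove dependence between neighbouring days.

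The reference to statistical power implies a test. Design treats each of the three participants as an independent test of the intervention, and each supplies four VAS series, so a per-series error rate bears directly on the conclusions. A reader would take the wording to mean that Tau-U needs no allowance for dependence. The regression is exposed too, to a lesser degree, whenever the check misses autocorrelation that is present.

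**Working it through.** The plan has no figure of its own to reproduce, so the check is a simulation under stated assumptions.

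**Inputs from the documents.** Daily ratings; baseline nA = 14, 21 or 28 (2, 3 or 4 weeks).

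**Assumptions.** Intervention nB = 35 or 42 daily ratings (six weekly sessions), giving 49 to 70 observations; complete data; stationary Gaussian AR(1) series with lag-1 autocorrelation phi, no phase effect and no trend; nominal 5% level.

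**Tau with the standard variance.** S is the sum of sign(B − A) over all baseline-intervention pairs, Tau = S/(nA·nB), and Var(S) = nA·nB·(nA+nB+1)/3.

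Worked case, nA = 21 and nB = 42:
- Var(S) = 21 × 42 × 64/3 = 18,816, so SD(S) = 137.2.
- SD(Tau) = 137.2/882 = 0.156, and the two-sided threshold is 1.96 × 0.156 = 0.305.
- At phi 0.3 the simulated variance of S is 1.75 times the formula value, so the true SD is √1.75 = 1.32 times larger. The threshold then lies only 1.96/1.32 = 1.48 true SDs from zero, and 2 × (1 − Φ(1.48)) is about 14%.
- At phi 0.2 the variance ratio is 1.44: 1.96/1.20 = 1.63, about 10%.
- At phi 0.5 the variance ratio is 2.69: 1.96/1.64 = 1.20, about 23%, against 23.9% in simulation for this case.

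All phase lengths, 20,000 series per setting:

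| phi | True SD / formula SD | Two-sided error | One-sided error | Baseline-corrected, two-sided |
|---|---|---|---|---|
| 0.2 | 1.20 | about 10% | about 9% | 10-13% |
| 0.3 | 1.30-1.33 | about 14% | about 11% | 14-17% |
| 0.5 | 1.63-1.66 | 24-25% | 16-17% | 23-27% |

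At phi 0 the uncorrected error is about 5%, so the formula is right under independence. At phi 0.1 it is about 7-8%. The baseline-corrected statistic is S minus the baseline S. Its range covers both leaving the variance unchanged and adding nA(nA−1)(2nA+5)/18.

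**Regression after a check.** Four-parameter level/slope model with the break fixed at the phase change, t on n−4 df, two-sided, 6,000 series per setting. OLS is replaced by REML AR(1) GLS when the check is positive. The plan names no check, so two were assumed:

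| Strategy | Detection at phi 0.2 / 0.3 / 0.5 | Level/slope error |
|---|---|---|
| Lag-1 residual correlation beyond 1.96/√n | 9-16% / 22-43% / 67-91% | 8-13% |
| One-sided 5% Durbin-Watson | 34-45% / 56-74% / 91-98% | 7-9% |
| AR(1) by REML always | not applicable | 5-8% (5-6% at phi 0) |

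**Repairs to Tau.**
- An AR(1) parametric bootstrap, with phi from the REML fit to the same series, holds two-sided error at 5-6% for phi 0 to 0.3 and 6-7% at 0.5, with or without baseline correction. A repeat run gave 7.5% in the shortest series at phi 0.5.
- A separate simulation (nB = 42) inflated the Tau variance by an AR(1) factor. Doing so always gave 4.9-5.5% at phi 0.2, 5.2-5.6% at 0.3 and 5.1-6.7% at 0.5. Doing so only after a positive lag-1 check gave 8.2-9.0%, 8.7-9.5% and 5.7-7.9%. Extending the plan's conditional trigger to Tau-U would therefore not be enough.

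**The case against.** The strongest reply is that the plan never commits to a Tau-U significance test. It speaks of effect sizes and published interpretation guidelines, and it writes out no p-value, interval or variance. If Tau-U is purely descriptive, error rates do not apply, and the estimate is centred in any case. This stands as a condition: the standard variance is inferred because no alternative is named. But a method chosen for its statistical power to decide whether ratings are higher is presented as a test, and the plan does not say otherwise.

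Other points stand in part:
- The question is directional, so the one-sided figures may be the relevant ones. They are smaller but still about double to triple the nominal level.
- The phi values are assumed, and at 0.1 the inflation is small. Missed days and bounded 10 cm ratings could change the figures.
- With a good check the gain from always fitting AR(1) is modest: 7-9% error falls to 5-8%. The larger regression error comes from an assumed weaker check, and the simulation did not estimate the breakpoint as the plan intends. For the regression, then, the firm point is that the check must be named. Always fitting AR(1) is simpler and slightly better.
- The source cited for the resistance claim could not be read and may concern the effect size only. If so, the sentence still misleads where it is placed, beside a claim of power.
- The regression does give a corrected analysis alongside Tau-U, but only as a complement and only when triggered.

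**Conclusion.** The concern holds and should be fixed before analysis. The stated resistance is not a property of standard Tau-U inference. The plan adjusts Tau-U only for trend, and its one remedy for dependence applies to a different analysis on an unspecified condition. For lag-1 autocorrelation between 0.2 and 0.5, the false-positive rate of a nominal 5% test is roughly two to five times nominal two-sided and about two to three times one-sided; at zero autocorrelation there is no inflation.

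This rests on the independence variance being the one used, on Tau-U p-values or intervals being reported, and on positive autocorrelation in complete daily series. Confidence is medium because the documents settle none of these three.

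**What to change.** 1. Delete the claim that Tau-U is resistant to autocorrelation.
2. Fit the piecewise GLS model with AR(1) errors by REML to every VAS series, with no preliminary test. If a check is kept, name the test and its threshold in advance.
3. State how Tau-U will be used. Either report it as a descriptive effect size without p-values, or take its p-value and interval from an AR(1) parametric bootstrap using the REML phi of the same series, with alpha and sidedness stated.

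This takes changes to the Analysis wording and a short piece of code; no new data are needed. The price is power. For a shift of one SD of the daily ratings, two-sided Tau power goes from 85-98% to 83-97% at phi 0. At phi 0.3 it goes from 80-94%, which is inflated by the excess false positives, to 60-82%.

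### The claim of strong Tau-U power is unsupported for this design: single-participant tests are weak for moderate or late mood gains, and a pooled, autocorrelation-adjusted Tau-U should be pre-specified

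*Combined protocol and SAP*

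**What the plan says.** Tau-U is the planned comparison of phases (Analysis): "To assess whether VAS ratings during the intervention phase are higher than baseline, Tau-U" is the method named. It is justified by the sentence "Resistant to autocorrelation, Tau-U provides strong statistical power in small datasets". Each participant is analysed alone, "with each participant serving as an independent test of the" intervention's effects (Design).

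The phase lengths follow from three places:
- Design: "Participants will be assigned to baseline durations of 2, 3, or 4 weeks".
- Idiographic Visual Analogue Scale: "Participants will rate their agreement with four daily statements on vertically presented 10 cm scales".
- Participants: "After the baseline phase, participants will attend six weekly sessions".

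The opening section expects wisdom to change first and mood last. Table 1 gives session 1 to information gathering and session 2 to psychoeducation and introducing the timeline. Reflection on timeline events begins in session 3.

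The plan gives no target effect, within-person SD, alpha, sidedness or power figure. It has no rule for reading a non-significant result in one participant and no estimate combined over participants. If lag-1 autocorrelation is detected, the stated remedy is GLS regression with an AR(1) structure, which does not alter the Tau-U test.

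**The concern.** The power of a phase comparison depends on the phase lengths, the size and timing of the effect, and the serial correlation. A general statement about small datasets cannot replace a calculation on these. If power is low for the effects that the plan itself considers plausible, a non-significant Tau-U says little about that participant. Beside a claim of strong power and a description of each case as an independent test, it could still be taken as a failed replication.

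The main mood question would then rest on three separate weak tests, although the same data could give one considerably more precise estimate. The first half of the quoted sentence matters too: if Tau-U is not in fact robust to serial correlation in daily ratings, its nominal 5% level and any interval built on it are too optimistic.

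**Working it through.** The plan states no power figure, so there is none to reproduce.

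**Inputs from the plan.** Baseline n_A = 14, 21 or 28 days (2, 3 or 4 weeks of daily ratings). Intervention n_B = 42 days (six weeks); it would be 35 if counted from session 1 to session 6.

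**Assumptions.** Two-sided 5%, normal ratings, no missing days, effects in within-person SD, one participant per baseline length. Ratings are independent in steps 1 to 5.

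**1. Standard error of Tau.** SE = sqrt[(n_A + n_B + 1) / (3 n_A n_B)].
- 14 days: sqrt(57/1764) = 0.180; 95% half-width 0.352
- 21 days: sqrt(64/2646) = 0.156; half-width 0.305
- 28 days: sqrt(71/3528) = 0.142; half-width 0.278

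**2. Immediate 0.5 SD shift.** Expected Tau = 2Φ(0.5/√2) − 1 = 0.276. Power ≈ Φ(Tau/SE − 1.96) gives 34%, 43% and 50%. Simulation of the Tau statistic agrees (33-34%, 43-44%, 49-51%).

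**3. Other patterns, simulated power.**

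| Effect | 14 days | 21 days | 28 days |
|---|---|---|---|
| 0.8 SD, immediate | 69-70% | 81-82% | 88-89% |
| 1.0 SD, immediate | 86-87% | 95% | 97% |
| Linear rise from day 1 to 1 SD | 34% | 42-43% | 49-51% |
| 1 SD starting on day 22 | 30% | 38% | 44% |
| Rise from session 3 to 1 SD at the end | 15-18% | 20-22% | 24-26% |

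The last pattern averages 0.5 × 28/42 = 0.33 SD over the phase, which is why power is so low. Tau-U with baseline-trend correction stays within about 4 points for the immediate shifts. With 35 intervention days, power is 33%, 41% and 47% at 0.5 SD and 68%, 79% and 86% at 0.8 SD.

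**4. Shift detectable with 80% power.** The two-means benchmark is 2.80 × sqrt(1/n_A + 1/42) = 0.86, 0.75 and 0.68 SD. The rank-type statistic needs slightly more. By simulation the shifts are about 0.9, 0.8 and 0.7 SD (at 28 days, power is 78% at 0.68 SD and 84% at 0.75 SD).

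**5. Pooled Tau.** The summed inverse variances are 30.9 + 41.3 + 49.7 = 122.0, so the pooled SE = 1/√122.0 = 0.0905.
- 0.5 SD shift: 0.276/0.0905 − 1.96 = 1.09, or 86%; simulation gives about 88%.
- Late rise: averaging 2Φ(δ_t/√2) − 1 over the 42 days, with δ_t = 0 to day 14 and (t − 14)/28 after it, gives Tau = 0.187. Then 0.187/0.0905 − 1.96 = 0.11, or 54%, as in simulation.

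**6. Autocorrelation.** With lag-1 correlation ρ the variance grows by roughly (1 + ρ)/(1 − ρ): 1.86 at 0.3 and 2.33 at 0.4. The nominal cut-off of 1.96 then acts as 1.96/√1.86 = 1.44 and 1.96/√2.33 = 1.28, so a true null is rejected in about 15% and 20% of cases. Simulation gives about 14% and 18%, for single and pooled tests alike. At a cut-off that restores 5%, single-participant power at ρ = 0.3 is 21%, 27% and 33% for 0.5 SD, and 67%, 76% and 84% for 1.0 SD.

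The same inflation applied to the pooled SE gives 0.0905 × 1.363 = 0.123 at ρ = 0.3 and 0.0905 × 1.528 = 0.138 at ρ = 0.4. Pooled power becomes about 61% and 52% for a 0.5 SD shift, and 33% and 27% for the late rise.

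**The case against.** The strongest reply is that the phase lengths are not poor in themselves. For an immediate, sustained shift with nearly independent ratings, power is 69-89% at 0.8 SD and 86-97% at 1.0 SD. The plan names no target effect, so treating 0.5 SD as important is an assumption. Its question is directional, and a one-sided test would raise power at 0.5 SD to 46%, 57% and 64%. This stands, and it limits the point to moderate, late or gradual effects and to the absence of a design-specific calculation.

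Tau-U is also not used alone. Visual analysis and piecewise regression of level and slope are planned, and regression is aimed at gradual change. It does not restore power, however: a joint test of level and slope change had only 12-18% for the late rise.

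Pooling is partly a matter of preference, because the design deliberately treats each case as its own test. That is a reason to show the pooled value beside the individual results, not to omit it.

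A reader might infer that the baselines are too short by the plan's own standard, since Design says that "five baseline data points are sufficient to distinguish natural fluctuations from intervention effects". The documents do not support this. Five is a cited minimum; 14 to 28 daily ratings are about 3 to 6 times that number.

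**Conclusion.** The point holds as a limit on the power claim. At the planned phase lengths, strong power in one participant applies only to large, immediate and sustained shifts, of about 0.9, 0.8 and 0.7 SD or more for 14, 21 and 28 baseline days. For a 0.5 SD shift it is about 33-51%, and for a rise from session 3 to 1 SD about 15-26%. A pooled Tau raises these to about 88% and 54% with independent ratings, and to less once serial correlation is allowed for. The claim of resistance to autocorrelation does not hold under positive lag-1 correlation of 0.3 to 0.4.

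These figures rest on assumed alpha, sidedness, effect sizes and correlation, because the plan states none of them. Missing ratings would lower power further. The late-rise pattern is compatible with the mood hypothesis but is not specified by it.

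A reader might also infer that a null in one participant will be misread as no effect. The documents are silent on how nulls are read, so the supportable statement is that such a null may be inconclusive and that the plan should say so.

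**What to change.** In the Analysis section:

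1. Limit the power statement to large, sustained shifts. State alpha and sidedness, and give the detectable shift for each baseline length under stated assumptions.
2. Remove or qualify the claim that Tau-U is resistant to autocorrelation.
3. Report each participant's Tau-U with a 95% interval, and state that a single non-significant result is not evidence of no effect.
4. Pre-specify one inverse-variance weighted Tau-U over the three participants for VAS_mood, shown beside the three individual results.
5. Build an autocorrelation allowance into the individual and pooled tests and intervals, for example a variance inflated by the estimated lag-1 correlation, or Tau computed on AR(1)-adjusted data. Name the method in advance.

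The cost is SAP wording and a small amount of calculation; no new data or participants are needed. There are two downsides. The pooled value averages over cases that may differ, so it must not replace the individual results. The autocorrelation allowance lowers the power quoted for independent ratings, for the pooled test from about 88% to about 61% at 0.5 SD if the lag-1 correlation is 0.3.
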